Intensive Social Interaction for Treatment of Post-Stroke Depression in Subacute Aphasia: The CONNECT Trial

Study Protocol

**[name]^{1, 2, 3 *}; [name]^{4, 5 *}; [name], MSc⁵;
[name], PhD²; [name], PhD⁶; [name]^{2, 7}**

¹ Faculty of Science, Medical School Berlin, Germany

² Department of Neurology, University Medicine Greifswald, Germany

³ Max Planck Institute for Human Cognitive and Brain Sciences, Leipzig, Germany

⁴ Department of Psychology, Freie Universität Berlin, Germany

⁵ Median-Klinik Berlin-Kladow, Germany

⁶ Psychologische Hochschule Berlin, Germany

⁷ German Centre for Neurodegenerative Diseases, Rostock and Greifswald, Germany

* Authors contributed equally.

Correspondence:

[name]. [name]
Medical School Berlin
Naturwissenschaftliche Fakultät
[name]
[name], Germany
E-mail: [contact]

Clinical Trial Registration:

www.clinicaltrials.gov; identifier: NCT04318951.

Last Update:

March 2019

Methods

Study design and setting

Following the CONSORT guidelines, we here present a parallel-group, blinded-assessment, quasi-randomised controlled phase-IIb trial^a in an outpatient rehabilitation centre in Berlin, Germany, between 2020 and 2022 (study acronym: CONNECT). This trial was approved by the ethics review board at University Medicine Greifswald, Germany (file number: BB 033/17). A team of neuropsychologists will obtain written informed consent from all participants, with ample time for questions and reflection to account for aphasia-immanent comprehension problems.

Study sample and power analysis

After routine referral to the study team, we will invite potential participants to a screening session to check their eligibility. Inclusion criteria will be: left-hemispheric cortical or subcortical ischemic or haemorrhagic event; subacute phase (0.5–6 months after the cerebrovascular lesion); German as first native language; right-handedness according to the Edinburgh Handedness Inventory;²⁹ diagnosis of PSD, as defined by international classification code F06.32;⁵ diagnosis of aphasia, as confirmed by the Bielefeld Aphasia Screening, with no more than two standard deviations below the average score on the subscale “Auditory Comprehension” to ensure understanding of basic instructions.³⁰ Exclusion criteria will be: other psychopathological or neurological conditions; premorbid history of recurrent depressive disorder; severe uncorrected vision or hearing that may prevent intensive social interaction during therapy or testing; serious non-verbal cognitive deficits, as revealed by the Corsi Block-Tapping Task.³¹

A target sample of 60 individuals will participate in the present phase-IIb trial. This sample size was calculated in an *a-priori* power analysis ($\alpha = 0.05$; $1-\beta = 0.80$; Cohen's $f = 0.390$; numerator degrees of freedom: 1; number of groups: 2; number of covariates: 2; resulting $n = 54$; expected dropout rate = 10%; final $n = 60$).³² Our effect size estimate derives from published phase-IIa RCT data on Beck's Depression Inventory (BDI), as specified below (converted from $\eta^2 = 0.132$).²⁰ Notably, an extended goal of the current phase-IIb trial will be to deliver a more precise effect size estimate for a subsequent phase-III RCT. We assumed a more conservative dropout rate for ILAT than seen in previous work.^{19,23}

^a Study on aspects of feasibility and potential efficacy as an intermediate step to a phase-III RCT.

Quasi-randomisation and blinding

Eligible candidates will be assigned to one of two treatment arms (each $n = 30$). Our ILAT protocol requires three individuals with aphasia to be present simultaneously in a rehabilitation centre for daily sessions over a 1-month treatment period. During the recruitment phase, occasionally fewer than three eligible candidates per treatment period will stay at the rehabilitation centre. To meet this logistical challenge in our phase-IIb trial—with a focus on treatment feasibility in PSD—candidates will receive ILAT only if enough fellow players are available to form groups of three individuals. Otherwise, candidates will receive the control intervention. The quasi-randomisation procedure will be administered by a person who does not participate in any stage of therapy or testing. A neuropsychologist with expertise in aphasia will perform all diagnostic sessions. This person will be blinded to group assignment and will not have patient contact aside from the testing. Data will be unmasked for final evaluation purposes by the study team who will not attend any of the therapy or testing sessions.

Treatment and procedures

ILAT requires individuals with aphasia to engage in everyday request and planning communication.¹⁸ Groups of three individuals and a therapist are seated around a table and provided with picture cards showing different objects (e.g., bottle) or action scenes (e.g., drinking). Barriers on the table prevent players from seeing each other's cards. Each card has a duplicate that belonged to one of the other players. The goal is to obtain this duplicate from a fellow player by requesting the depicted object (e.g., “Give me the [...]”) or by proposing an action based on the visualised scene (e.g., “Let's [...] together”). The rich turn-taking structure of ILAT serves as a vehicle for intensive use of formulaic expressions: (i) If the duplicate is available, the players compare the depicted objects or scenes; in the case of a match, the addressee hands over the corresponding card to the person who initiated the request or action-planning sequence (e.g., “Here you are”—“Thank you”—“You're welcome”). (ii) If the duplicate is not available, the addressee rejects the request or proposed action (e.g., “I'm sorry”—“No problem”—“Too bad”). (iii) In the event of misunderstandings, the players ask clarifying questions (e.g., “Pardon me?”).

We will recreate training materials and procedures described previously.²³ The therapist will continuously apply positive reinforcement via encouraging feedback to diminish the likelihood of cognitive-affective distress caused by lack of social stimulation, in line with a common model of depression aetiology.¹ Practical experience with ILAT demonstrates that players often imitate the therapists' behaviour by starting to support one another verbally, thus

multiplying the amount of positive reinforcement exchanged during treatment (e.g., “Well done!”). Self-cueing strategies will be allowed, along with gestures to accompany—but not replace—spoken language. ILAT involves five weekly sessions, each with a duration of one hour, over a total treatment period of one calendar month. We do not set a minimum amount of treatment in our protocol to compensate for missed sessions, since dropout rates for ILAT have been extremely low in prior work.^{19, 23} The treatment will be delivered by a team of speech-language therapists and neuropsychologists who will receive training and continuous supervision before and during the trial.

Standard care will conform to state-of-the-art procedures of rehabilitation centres certified in Germany. Depending on the participants’ diagnoses and needs, standard care will include: antidepressant medication (drug and dosage defined individually by a physician blinded to group randomisation and study purpose; substance classes: selective serotonin reuptake inhibitors, tri- and tetracyclics), occupational therapy (2–3 hours weekly), physiotherapy (2–3 hours weekly), and non-intensive speech-language therapy (2–3 hours weekly with emphasis on phonology, lexicon and syntax, as detailed in a large-scale RCT protocol³³).

Outcomes and testing

Feasibility, our *primary* outcome, will be considered to be met if at least two-thirds of participants in Group I complete all ILAT sessions offered during the 1-month treatment period.

As a *co-primary* outcome of potential efficacy, we will administer a 20-item version of the BDI.³⁴ This self-report measure is known for its excellent psychometric properties, including construct validity and test-retest reliability, in individuals *without* aphasia. The BDI has been successfully piloted in individuals *with* aphasia, as indicated by phase-IIA RCT data.²⁰ To complement the BDI, we will use a clinician-rated measure with good psychometric properties as an additional *co-primary* outcome, a 7-item version of the Hamilton Rating Scale for Depression.³⁵

Reflecting the potential influence of treatment-induced or spontaneous progress in verbal expression on change in depression severity, we will employ the combined Aachen Aphasia Test (AAT) subscales “Repetition” and “Naming” as a *secondary* outcome and covariate in our analyses.³⁶ These two AAT subscales proved to be most sensitive to ILAT-mediated gains in chronic aphasia, as shown by RCT data.^{19, 23} Moreover, participants will complete the Self-Efficacy Questionnaire, a self-report measure conceived to quantify personal confidence in overcoming obstacles when accomplishing difficult tasks.³⁷ Low scores on this *secondary*

outcome constitute a risk factor for cognitive-affective distress, suggesting a significant negative relationship between results on the Self-Efficacy Questionnaire and BDI.³⁸ The Self-Efficacy Questionnaire will provide an external criterion to determine the psychometric adequacy of our self-report co-primary outcome, the BDI, in individuals with aphasia, given the possibility of serious deficits in understanding spoken instructions not ruled out during eligibility screening, as specified above.

A neuropsychologist blinded to group allocation will conduct all diagnostic sessions. The neuropsychologist will have substantial experience in communication with individuals suffering from aphasia-immanent comprehension problems. Testing will take place immediately before (baseline: T₁; BDI, HAM-D, and AAT) and within 24 hours after the 1-month treatment period (endpoint: T₂; BDI, HAM-D, AAT, and Self-Efficacy Questionnaire).

References

- 1 Lewinsohn PM. A behavioral approach to depression. Friedman RJ, Katz MM, editors. In: *Psychology of Depression: Contemporary Theory and Research*. Wiley; 1974. p. 157–178.

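### ILAT is delivered in groups of three, but the sample size assumes independent patients and no rule brings the groups into the BDI or HAM-D analysis

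*Combined protocol and SAP*

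**What the plan says.** The section on quasi-randomisation and blinding makes the trio the unit of delivery: "candidates will receive ILAT only if enough fellow players are available to form groups of three individuals". Everyone else receives the control intervention. The section on treatment and procedures describes the setting: "Groups of three individuals and a therapist are seated around a table". It expects players to take up the therapist's supportive behaviour, "multiplying the amount of positive reinforcement exchanged during treatment", and says that ILAT is "delivered by a team of speech-language therapists and neuropsychologists". Standard care is described by each participant's diagnoses and needs, and no grouping is mentioned.

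The section on study sample and power analysis lists alpha 0.05, power 0.80, Cohen's f 0.390, one numerator degree of freedom, "number of groups: 2; number of covariates: 2", a resulting n of 54 and a final n of 60 after 10% dropout. It has no ICC, design effect or number of trios. The same section says that the trial should "deliver a more precise effect size estimate for a subsequent phase-III RCT".

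There is no statistical analysis section. The only statement about the efficacy model, under outcomes and testing, is that the AAT score serves as a covariate.

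**The concern.** Three patients who share a table, a therapist and a calendar month of five weekly sessions may end with more similar mood scores than three patients from different groups. The protocol itself describes mutual reinforcement as part of how ILAT works. If outcomes within a trio are positively correlated, the mean of 27 ILAT patients is less precise than the mean of 27 independent patients. The power inputs point to an analysis that does not allow for this.

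What is at stake is the standard error of the efficacy co-primaries. An interval that is too narrow would accompany the effect estimate handed to phase III. Phase III would also lack an ICC estimate, which it needs for its own sample size if ILAT is again given in groups.

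**Working it through.** **Inputs from the protocol.** Alpha 0.05; f = 0.390 (from eta squared 0.132: √(0.132/0.868) = 0.390); 2 groups; 2 covariates; 54 analysed; 60 enrolled; 30 per arm; ILAT groups of three.

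**Assumptions.** ICC 0.05, 0.10 or 0.20; trios fixed for the month; controls ungrouped; equal arms; total variance 1 in each arm, so the mean difference is 2f = 0.78.

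**1. The plan's own figure.** Noncentral F with λ = f²N and denominator df = N − 4.
- N = 54: λ = 0.1521 × 54 = 8.21, df 50, power 0.8025.
- N = 53: power 0.795.
- N = 60: power 0.8435.

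So 54 is exactly the independent-patient answer, and 54/0.9 = 60.

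**2. Variance with trios.** For n patients per arm and trio sizes m:
- ILAT mean: v1 = [1 + ICC × (Σm²/n − 1)]/n
- control mean: v2 = 1/n
- λ = 0.78²/(v1 + v2)

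Full trios give Σm²/n = 3, so v1 = (1 + 2 ICC)/n. Example for n = 27 and ICC 0.10: v1 = 1.2/27 = 0.0444, v2 = 0.0370, λ = 0.6084/0.0815 = 7.47.

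With 30 assigned and 3 ILAT patients lost from different trios, 7 trios of three and 3 of two remain, and Σm²/n = (63 + 12)/27 = 2.78.

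**3. Analysis that ignores trios (9 full trios, 54 analysed).** The true standard error exceeds the independence-based one by the factor √[(2 + 2 ICC)/2] = √(1 + ICC) = 1.025, 1.049, 1.095. The reported standard error is therefore about 2%, 5% and 9% too small. Type I error is close to P(|t| > 2.007/√(1 + ICC)) on 52 df: about 5.6%, 6.1% and 7.3%. Simulation agrees to within about 0.3 percentage points. The simulated rejection rate under the planned effect is about 0.80, 0.79 and 0.78.

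**4. Analysis that accounts for trios.** Variance inflation alone keeps df = N − 4. Satterthwaite df = (v1 + v2)²/[v1²/(K − 1) + v2²/(n − 1)], with K trios.

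| Case | Power basis | ICC 0.05 | ICC 0.10 | ICC 0.20 |
|---|---|---|---|---|
| 54, 9 full trios | variance only | 0.783 | 0.764 | 0.728 |
| 54, 9 full trios | Satterthwaite (df 23.2, 22.2, 20.3) | 0.764 | 0.743 | 0.702 |
| 54, 10 depleted trios | variance only | 0.785 | 0.768 | 0.736 |
| 54, 10 depleted trios | Satterthwaite (df 25.6, 24.6, 22.9) | 0.770 | 0.751 | 0.715 |
| 60, 10 full trios | variance only | 0.826 | 0.808 | 0.773 |
| 60, 10 full trios | Satterthwaite (df 26.1, 24.9, 22.8) | 0.810 | 0.790 | 0.752 |

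Part of the loss is a pure df cost: at ICC 0 with 54 analysed, Satterthwaite df give 0.786 (9 trios) or 0.789 (10 trios) instead of 0.8025. Subtracting two further df for the covariates changes power by less than 0.005.

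**The case against.** The strongest reply is that the ICC is not in the documents, that mutual support could raise mood in every trio without making trios differ from one another, and that adjustment for two covariates could shrink whatever correlation exists. This stands as a limit on the size of the effect, and is why a range is given. It does not justify assuming a correlation of exactly zero without saying so.

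A second reply is about weight. Feasibility is the primary outcome, efficacy is only potential at this stage, and the missing trio term is part of a wider gap: no efficacy model is written down. This also stands, and it caps the importance of the point. BDI and HAM-D are nevertheless named co-primary outcomes.

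A reader might infer more than the documents support:
- **That the planned test has power of only 0.70 to 0.78.** Those figures belong to an analysis that adjusts for trios. The inferred unadjusted test still rejects in about 0.80 to 0.78 of trials; its fault is the standard error and the type I error.
- **That any positive correlation takes power at 54 below 80%.** With variance inflation alone, power stays at 0.80 up to an ICC of about 0.006.
- **That power at ICC 0.05 falls to 0.75.** That value arises in simulation only when the trio variance is truncated at zero. It reflects the estimator; the Satterthwaite values are 0.76 to 0.77.
- **That trio membership rotates.** The section on quasi-randomisation and blinding asks for three people present together for daily sessions over the treatment period, which reads most naturally as a fixed trio.

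**Conclusion.** The point holds and is of moderate importance. Delivery in trios is a stated design feature, the sample size ignores it, and nothing prespecifies how it enters the efficacy analysis. Under the assumed ICCs the consequence takes one of two forms: a modest excess of type I error with too narrow an interval if trios are ignored, or power at 54 some 2 to 10 percentage points below the stated 0.80 if they are modelled. If all 60 were analysed, modelled power would be 0.83, 0.81 and 0.77 from variance inflation alone, or 0.81, 0.79 and 0.75 with Satterthwaite df. The enrolled sample thus absorbs much of the loss at the lower ICCs, provided dropout is small.

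These sizes rest on the assumed ICCs, fixed trios, ungrouped controls and equal total variance in the two arms. If trio variance were instead added to an equal residual variance, variance-only power at 54 would be about 0.77 at ICC 0.05 and 0.67 at ICC 0.20. Whether the pilot effect size already reflects grouped delivery cannot be checked from the documents.

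A reader might also take this as a finding about allocation by availability. It is not: a trio term does nothing about any bias from that source, which is a separate matter.

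**What to change.** 1. Record trio membership and treating therapist for every ILAT patient, and confirm that control care is not grouped.
2. For BDI and HAM-D, prespecify a partially nested analysis: a trio effect in the ILAT arm only, controls as singletons, separate residual variances by arm, and Satterthwaite or Kenward-Roger df. Allow the trio variance estimate to be negative. With 9 to 10 trios it falls at or below zero in about 43% to 44% of simulated trials at ICC 0.05 and 20% to 22% at ICC 0.20. Truncation at zero would make the test conservative, with type I error about 4.2% to 4.8%.
3. Report the estimated ICC with its interval for phase III planning.
4. Restate power along these lines: *Power assumes f = 0.390, fixed groups of three in the ILAT arm, ungrouped controls and an assumed ICC of 0.05, 0.10 or 0.20. With 54 analysed it is about 0.78, 0.76 or 0.73 from variance inflation alone, and 0.76 to 0.77, 0.74 to 0.75 or 0.70 to 0.72 with Satterthwaite df on 9 to 10 groups. With 60 analysed it is 0.83, 0.81 or 0.77, and 0.81, 0.79 or 0.75, respectively.*

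The cost is slightly more analysis work and a lower stated power. If the true ICC is 0, power at 54 is about 0.79 instead of 0.80. No patients are added and treatment does not change.

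### No rule says who enters ILAT when candidates outnumber trio places, and the efficacy covariates are not fixed, so the BDI and HAM-D comparison is open to bias of unknown size

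*Combined protocol and SAP*

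**What the plan says.** All places are in the combined protocol and SAP.

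- **Allocation** (*Quasi-randomisation and blinding*). The section opens with "Eligible candidates will be assigned to one of two treatment arms", 30 in each. The rule is that "candidates will receive ILAT only if enough fellow players are available to form groups of three individuals. Otherwise, candidates will receive the control intervention". The reason given is that "occasionally fewer than three eligible candidates per treatment period will stay at the rehabilitation centre". On who runs it: "The quasi-randomisation procedure will be administered by a person who does not participate in any stage of therapy or testing". The outcome assessor is blinded.
- **Power** (*Study sample and power analysis*). The inputs are alpha 0.05, power 0.80, Cohen's f = 0.390 and "number of covariates: 2", giving 54, raised to 60 for 10% dropout. The covariates are not named. A further aim is to "deliver a more precise effect size estimate for a subsequent phase-III RCT". Patients enter from 0.5 to 6 months after the lesion.
- **Outcomes** (*Outcomes and testing*). Feasibility is primary and is judged in the ILAT arm only, as the share who complete every session offered. BDI and HAM-D are co-primary for potential efficacy. The combined AAT Repetition and Naming score is both a secondary outcome and a covariate. The reason given is that language gains, whether produced by therapy or spontaneous, may influence change in depression. BDI, HAM-D and AAT are measured at T1 and T2.

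**The concern.** The allocation rule contains no chance mechanism. With fewer than three candidates, everyone goes to control. With more candidates than trio places, the rule gives those left over a destination, control, but does not say how they are picked. An administrator with no written rule could, knowingly or not, place the more able, more motivated or less depressed patients in the trio. That would bias the BDI and HAM-D comparison. It could also raise the completion rate on which feasibility is judged.

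A second route is that arm follows the number of patients present in a given period, and so follows calendar time. This confounds only if caseload is related to prognosis.

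In a design of this kind, adjustment has to do work that randomisation would otherwise do, yet the adjustment set is not fixed. On the natural reading, no baseline depression score is named as a covariate. The AAT visit is also open. Adjusting for AAT at T2, or for its change, would estimate the effect net of language gain and not the total effect of ILAT. These are different quantities to carry into phase III.

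**Working it through.** **1. The plan's own figure.** Inputs from *Study sample and power analysis*: f = √(0.132/0.868) = 0.390, two groups, two covariates. ANCOVA power comes from the noncentral F with λ = f²N, df1 = 1 and df2 = N − 2 − covariates.

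- N = 54: λ = 0.1521 × 54 = 8.21, df2 = 50, power 0.8025. N = 53 gives 0.7948. The minimum is therefore 54, and 54/0.9 = 60. Both figures reproduce.
- The minimum N is 54 with zero, one, two or three covariates, so the sample size does not reveal what the covariates are.

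**2. Where the 30 controls come from.** Assume every trio member is a trial candidate, each candidate belongs to one period, and nobody is carried over.

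- Thirty ILAT places are 30/3 = 10 trios, so at most 10 periods contain a trio.
- A short period supplies at most two controls. If all 30 controls came from short periods, there would be at least 30/2 = 15 of them, which is 15/(15 + 10) = 60% or more of all periods. That does not fit a shortage described as occasional.
- Suppose instead one trio per period and a shortage in one period in three (an assumed reading). Five short periods beside ten with a trio supply at most 10 controls, so at least 20 of the 30 would be surplus candidates.

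On the protocol's own description, the unwritten selection step could therefore fill much of the control arm.

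**3. What a residual imbalance would do (assumed sizes).** With no true effect, 27 per arm and two covariates, λ = δ² × 27 × 27/54 = 13.5δ².

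| Assumed imbalance δ (SD) | λ | Rejection rate at nominal 5% |
|---|---|---|
| 0.1 | 0.135 | 6.5% |
| 0.2 | 0.54 | 11.1% |
| 0.3 | 1.215 | 19.1% |

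The documents give no value for δ and no sign.

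**4. Power is a minor matter.** With d = 2f = 0.78 and λ = d² × n1 × n2/N, power at N = 54 is 0.798 for a 24:30 split, 0.782 for 21:33 and 0.755 for 18:36. Near the stated 1:1 target the loss is negligible.

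**5. How far a draw by lot would reach (assumed Poisson arrivals, one start per month).** The trial runs "in Berlin, Germany, between 2020 and 2022". Taking that as 24 to 36 months, 60 patients are 60/24 = 2.5 to 60/36 = 1.67 per period. A mean of 4 is added because it makes shortages less frequent, although 60/4 = 15 periods would then suffice. The reach of a draw is the share of candidates in periods with a surplus. With one trio per period this is N > 3; with several trios it is N > 3 and not a multiple of three.

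| Mean per period | Periods with fewer than three | Reach, one trio | Reach, several trios |
|---|---|---|---|
| 1.67 | 77% | 23% | 21% |
| 2.5 | 54% | 46% | 39% |
| 4 | 24% | 76% | 57% |

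The remainder, from 100 − 76 = 24% to 100 − 21 = 79% of candidates, would still be assigned by caseload alone.

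**6. Cost of fuller adjustment.** At N = 54 and 1:1, power is 0.8025 with two covariates, 0.8022 with three and 0.8018 with four.

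**The case against.** The design is openly labelled quasi-randomised, phase IIb, and aimed at feasibility and potential efficacy ahead of a phase-III RCT. Trios are a logistical need. The administrator is independent and the assessor blinded. All of this is true and limits selective choice and assessment bias. None of it supplies a selection rule or makes the arms comparable.

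Several stronger readings are tempting and should not be drawn.

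- *Surplus candidates are left without an arm.* They are not: the text sends them to control. Only the choice among candidates is missing.
- *Confounding by caseload is established.* No document links the number of patients present to prognosis. The wide time-since-stroke window and the acceptance of spontaneous progress concern prognosis alone.
- *Feasibility is untouched, or is compromised.* It does not depend on the between-arm comparison, but ungoverned entry to ILAT could favour completers. The documents show no more than that possibility.
- *The trial is underpowered.* That needs a markedly uneven split, whereas the protocol sets 30 per arm. The arrival model is an assumption, and its lower rates do not fit occasional shortages.
- *Exactly one covariate is missing.* Two could be counted from the two AAT subscales or the two visits. The word combined favours a single AAT covariate. On either alternative, baseline BDI and HAM-D would still not be named.
- *Only baseline AAT is legitimate.* The protocol ties this covariate to progress in verbal expression, which a T1 score cannot capture. An effect net of language change is a valid question, but the plan has to say which question it is asking.

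**Conclusion.** The concern holds in this form: allocation has no stated random element, selection among surplus candidates is ungoverned, and the covariates and the AAT visit are not fixed. The co-primary efficacy estimate intended for phase III is therefore exposed to bias whose direction and size cannot be derived from the documents. The error rates and draw-reach figures above rest on assumed imbalances and arrivals and only show scale. The claim that surplus selection is the more important route rests on the 30-per-arm target, groups of three and shortages being occasional, under the assumptions stated with that count. The plan should be changed, but nothing here shows that the comparison is in fact biased. Confidence is medium.

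**What to change.** 1. **Allocation.** When candidates exceed trio places, draw by lot who enters ILAT, using a pre-generated list held by the independent administrator. State how many trios may run in one period.
2. **Main efficacy analysis.** Define it as the total effect, for phase-III use: ANCOVA of T2 BDI and of T2 HAM-D, each adjusted for the T1 score of the same scale, T1 AAT and time since stroke. Add start date in a sensitivity analysis. Restate the power input as three covariates. Keep the protocol's interest in language progress as a separate analysis adjusted for AAT progress, labelled as the effect net of language change.
3. **Reporting.** Present the between-arm effect as a non-randomised estimate and carry that caveat into phase-III planning.

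The cost is protocol wording, a random list and one degree of freedom: 0.8025 − 0.8022 = 0.0003 of power at N = 54. The T1 scores are already collected, and time since stroke is known from eligibility screening. Trios stay as planned. The limit of the remedy is that candidates in periods without a surplus are still assigned by caseload, so the confounding is only partly removed.

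### Antidepressant use can differ between non-randomised arms, yet medication is neither a named covariate nor a listed T1 measurement, so the BDI and HAM-D contrasts may be biased in either direction.

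*Combined protocol and SAP*

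**What the plan says.** The document is the combined protocol and SAP; its sections are unnumbered.

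- **Population** (Study sample and power analysis). Entry requires "diagnosis of PSD, as defined by international classification code F06.32".
- **Medication** (Treatment and procedures). "Depending on the participants’ diagnoses and needs, standard care will include: antidepressant medication", with "drug and dosage defined individually by a physician blinded to group randomisation and study purpose". Use therefore varies from patient to patient. That the ILAT arm also receives standard care is implied by the prescriber's blinding but is not stated outright.
- **Assignment** (Quasi-randomisation and blinding). Of the planned 30 per arm, "candidates will receive ILAT only if enough fellow players are available to form groups of three individuals". "Otherwise, candidates will receive the control intervention".
- **Outcomes** (Outcomes and testing). Feasibility is primary. For efficacy, "we will administer a 20-item version of the BDI" as a co-primary, alongside a 7-item Hamilton scale.
- **Covariates.** The combined AAT Repetition and Naming score is described as a secondary "outcome and covariate in our analyses" (Outcomes and testing). The power analysis counts two covariates and names neither.
- **Measurements.** T1 comprises BDI, HAM-D and AAT. Medication is not a listed measurement at T1 or T2, an eligibility limit, an allocation factor or a named analysis term. No balance check or sensitivity analysis for it is described.

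**The concern.** Antidepressants are given to change what the BDI and HAM-D measure. Under chance allocation, unequal use between arms would be random error, already covered by the p-value and confidence interval. Here assignment follows the availability of fellow players, so no such guarantee applies. Anything that varies with availability, such as case mix, severity, time since stroke or prescribing habits, could also shift drug use between arms. If the model contains no medication term, that shift stays in the ILAT contrast.

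The plan also aims to supply a more precise effect size for a phase-III trial, so even a moderate bias would reach something the trial is meant to deliver.

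**Working it through.** **1. The plan's own figure.** Inputs from Study sample and power analysis: eta squared 0.132, alpha 0.05, power 0.80, 1 numerator df, 2 groups, 2 covariates.

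- f = sqrt(0.132 / 0.868) = 0.390. For two equal groups, d = 2f = 0.78.
- Power comes from the noncentral F distribution with lambda = N × f² and df = (1, N − 2 − 2).
- N = 53 gives 0.795. N = 54 gives lambda = 54 × 0.1521 = 8.21 and power 0.8025.
- 54 / 0.90 = 60.

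The stated 54 and 60 reproduce; the sample size is not in dispute.

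**2. Size of a possible bias (assumed inputs).** The documents give no usage rate, no gap between arms and no drug effect. Assume a gap in use of 10 to 40 percentage points and a drug effect of 0.2 to 0.5 SD, in the same SD units as d.

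Bias = gap × drug effect. The type I error is the power function above with f = bias / 2, N = 54 and df = (1, 50), when ILAT has no true effect.

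| Gap | Drug effect (SD) | Bias (SD) | Share of 0.78 | Type I error |
|---|---|---|---|---|
| 0.10 | 0.2 | 0.02 | 3% | 5.1% |
| 0.20 | 0.4 | 0.08 | 10% | 6.0% |
| 0.40 | 0.5 | 0.20 | 26% | 11.1% |

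**3. Is a 20-point gap implausible?** With 30 per arm and 50% use (assumed), the standard error of the difference is sqrt(2 × 0.25 / 30) = 0.129. Even under true randomisation, a gap of 20 points or more would arise with probability of about 12% (normal approximation). This shows only that such a gap is not extreme. It is not evidence that this design produces one.

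**4. Cost of adding a T1 medication covariate.** Three covariates at N = 54 give df = (1, 49).

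- Use balanced between arms: power 0.8022, against 0.8025 with two covariates.
- Use unbalanced: lambda is multiplied by (1 − r²), where r is the correlation of medication with arm. With 50% use overall and equal arms, r equals the gap.
- 20 points: lambda = 8.21 × 0.96 = 7.88, power 0.786.
- 30 points: lambda = 8.21 × 0.91 = 7.47, power 0.764.

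These powers ignore any gain from outcome variance that medication explains.

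**The case against.** **The prescriber is blinded to group and study purpose.** This is a real safeguard against prescribing driven by knowledge of the arm, and it protects most for drugs started after T1. It cannot equalise use that already differs at T1.

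**The second covariate might be medication.** A reader might infer that the plan excludes a medication term. The documents do not support that: two covariates are counted and one is unidentified, so the exact statement is that none is named. The T1 score is an equally open candidate. If it is the T1 score, the gap remains: two patients with equal T1 scores, one recently started on a drug and one untreated, can have different expected change over a month.

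**The illustration overstates what adjustment can repair.** This stands. In patients already treated at T1, part of the drug effect is already in the T1 score. Patients who start after T1 are missed by a T1 yes/no term.

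**Imbalance is not shown.** Also correct. A reader might infer that whole months belong to one arm, so that calendar changes pass straight into the comparison. The plan says only that there will occasionally be fewer than three candidates, and nothing links the number of fellow players to antidepressant use.

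**Medication is one confounder among several.** True. Time since stroke (0.5 to 6 months) and baseline severity are others, and the allocation is the root cause. Medication still merits its own line because it acts on the co-primary outcomes and is easy to record.

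**Conclusion.** The concern holds in limited form. In a comparison not formed by chance, the plan names no term for a treatment that can affect both depression co-primaries, and does not list it for measurement at T1. A baseline difference in use could bias the BDI and HAM-D contrasts and the effect estimate carried to phase III.

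The 0.02 to 0.20 SD and 5.1 to 11.1% rest wholly on the assumed gap and drug effect, and only the share due to baseline use is removable by T1 adjustment. Within these ranges, medication could not by itself produce d = 0.78.

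Two stronger readings are not supported. One is that a drug difference would manufacture an apparent ILAT benefit: the direction is unknown, and imbalance could equally hide one. The other is a larger bias. A 0.8 SD drug effect with a 30-point gap would give 0.24 SD and a type I error of 13.9%, but that drug effect exceeds the whole planned ILAT effect and nothing in the documents supports it.

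The feasibility outcome, defined by session completion, is not affected.

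**What to change.** - Name both covariates in the efficacy models.
- Take antidepressant status at T1 (yes/no) from the chart. Pre-specify it, with the T1 score of the outcome, as a baseline covariate in the BDI and HAM-D models.
- Tabulate T1 use, and starts, stops and dose changes between T1 and T2, by arm.
- Keep changes after T1 out of the main model. Label any analysis restricted to patients with unchanged medication as exploratory, because it conditions on events after allocation.
- State explicitly whether the ILAT arm also receives standard care.

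This is a cheap improvement. The covariate needs one chart item and one degree of freedom; the table of later changes needs a second look at the same charts. The power cost is negligible only if use is balanced. At a 20- or 30-point gap, power falls to about 0.79 or 0.76, before any gain from variance explained. Adjustment does not repair the non-random allocation or deal with other confounders.
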